STATISTICAL CONSIDERATIONS	
The primary focus of this trial will be in the evaluation of PD-L1 to predict outcome and, also, secondarily to use the PRP model as a basis for outcome prediction. We expect that about 45% (or 54 expected) patients will have 0% PD-L1 and roughly 15% (or 18 expected) patients will express PD-L1 > 20%, which, given the sample size of 120 ccRCC patients provides 90% power using a 0.05 level two-sided test to test the hypothesis that PD-L1 >20% will be associated with significantly improved 1-year PFS rate for patients treated with PD-1 blockade (55% vs 13% taken as a binomial quantity). Considering the four groups of PD-L1 expression (0%, 1-5%, 5-20%, >20%), and with an expected patient allocation within groups of (45%, 25%, 15%, 15%), the Cochran-Armitage test gives at least 90% power to detect a trend in 1-year PFS of (13%, 19%, 35%, 55%) using a two-sided 0.05 level test for trend. Modest changes in the proportions of patients in the various PD-L1 categories will not substantially affect the power. For example, if the distribution across PD-L1 categories is [25%, 25%, 25%, 25%] rather than the anticipated [45%, 25%, 15%, 15%] the power for the trend test remains greater than 90%.
 
As a secondary objective, we will apply the PRP model, developed in the DF/HCC Kidney SPORE Project 4, to assign each patient a probability of having PFS > 1 year. This will be assessed by both RECIST and irRECIST. The validity of the model will be assessed by the Brier score as well as via evaluation of the AUC. The exact distribution is unknown, but assuming an overall 1-year PFS of 28% and that 40% of patients are expected to be “positive” by the PRP model, 120 ccRCC patients give 90% power to detect a 29% higher 1-year PFS between 48 positive patients and 72 negative patients (via Fisher’s exact test and assuming a difference in PFS of 46% vs 17%). All testing above will be done at 1-sided $\alpha = 0.025$. The specific distributional breakdowns are unknown but the power is relatively robust. For example, if the split between positive and negative is more even (50/50) then power for the above difference in 1-yr PFS remains over 90%. If the actual difference in 1-yr PFS is smaller than anticipated for example 25% (44% vs 19%) then the test will still have at least 80% power.
 
At this time, 10 fresh frozen baseline tumor specimens and 3 pairs of specimens have been collected with an additional patient likely to be collected before accrual of the original 120 patients is complete. Therefore, fourteen additional patients are to be enrolled to collect fresh frozen specimens necessary to provide 25 baseline and 15 paired baseline and resistant fresh frozen samples to be used for single cell RNAseq experiments aimed at identifying factors associated to resistance as outlined in the DOD Translational

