12. STATISTICAL METHODS

12.1 Part A Primary Endpoint

The primary focus of this trial will be in the evaluation of PD-L1 to predict outcome and, also, secondarily to use the PRP model as a basis for outcome prediction. We expect that about 45% (or 54 expected) patients will have 0% PD-L1 and roughly 15% (or 18 expected) patients will express PD-L1 > 20%, which, given the sample size of 120 ccRCC patients provides 90% power using a 0.05 level two-sided test to test the hypothesis that PD-L1 > 20% will be associated with significantly improved 1-year PFS rate for patients treated with PD-1 blockade (55% vs 13% taken as a binomial quantity). Considering the four groups of PD-L1 expression (0%, 1-5%, 5-20%, >20%), and with an expected patient allocation within groups of (45%, 25%, 15%, 15%),

the Cochran-Armitage test gives at least 90% power to detect a trend in 1-year PFS of (13%, 19%, 35%, 55%) using a two-sided 0.05 level test for trend. Modest changes in the proportions of patients in the various PD-L1 categories will not substantially affect the power. For example, if the distribution across PD-L1 categories is [25%, 25%, 25%, 25%] rather than the anticipated [45%, 25%, 15%, 15%] the power for the trend test remains greater than 90%.

As a secondary objective, we will apply the PRP model, developed in the DF/HCC Kidney SPORE Project 4, to assign each patient a probability of having PFS >1 year. The validity of the model will be assessed by the Brier score as well as via evaluation of the AUC. The exact distribution is unknown, but assuming an overall 1-year PFS of 28% and that 40% of patients are expected to be “positive” by the PRP model, 120 ccRCC patients give 90% power to detect a 29% higher 1-year PFS between 48 positive patients and 72 negative patients (via Fisher’s exact test and assuming a difference in PFS of 46% vs 17%). All testing above will be done at 1-sided $\alpha=0.025$. The specific distributional breakdowns are unknown but the power is relatively robust. For example, if the split between positive and negative is more even (50/50) then power for the above difference in 1-yr PFS remains over 90%. If the actual difference in 1-yr PFS is smaller than anticipated for example 25% (44% vs 19%) then the test will still have at least 80% power.

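### At N=120 and one-sided 0.025, Fisher's exact test for PRP positive versus negative has about 79% power for 44% v 19%, slightly below the stated 80%

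*Combined protocol and SAP*

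**What the plan says.** Section 12.1 (Part A Primary Endpoint) gives the power for the secondary PRP comparison, and the Statistical Considerations part of the synopsis repeats it.

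- **Sample size and main effect:** "120 ccRCC patients give 90% power to detect a 29% higher 1-year PFS between 48 positive patients and 72 negative patients".
- **Test:** "via Fisher’s exact test and assuming a difference in PFS of 46% vs 17" per cent.
- **Level:** "All testing above will be done at 1-sided" alpha = 0.025. Earlier in the same section the PD-L1 trend test is described as "using a two-sided 0.05 level test for trend".
- **Robustness to the split:** power for 46% v 17% is said to stay above 90% if positives and negatives divide 50/50.
- **Robustness to the effect:** "for example 25% (44% vs 19%) then the test will still have at least 80% power". The split that applies to this sentence is not restated.

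The number of ccRCC patients differs between sections. The power text and section 12.6 use 120. The synopsis and section 5 plan 134, and the accrual goals and section 12.5 explain the extra 14 as a source of fresh frozen tissue for single-cell RNA sequencing. Section 12.8 takes all eligible registered subjects as the primary analysis population, and section 12.10 assesses all registered ccRCC subjects for 1-year PFS.

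**The concern.** The 80% is written as a lower bound and tied to a named test and level. Fisher's test is discrete and conservative, so its power can fall below what a normal approximation suggests. A claim that lands exactly on a round threshold is therefore worth enumerating. If the bound fails under the plan's own test, level and N, the documents overstate, however slightly, how robust the PRP comparison is to a smaller effect. The same conservatism raises a second question: whether some power could be recovered without adding patients.

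**Working it through.** **Inputs** (section 12.1): n1 = 48 PRP positive, n2 = 72 PRP negative; Fisher's exact test; one-sided 0.025; 1-year PFS of 46% v 17% (main) and 44% v 19% (smaller effect); alternative split 60/60. From the synopsis accrual goals: 134 planned ccRCC patients.

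**Method.** Let X ~ Bin(n1, p1) and Y ~ Bin(n2, p2). For each pair (x, y), the one-sided Fisher p-value is P(H ≥ x), where H is hypergeometric with population n1 + n2, x + y patients progression-free and n1 drawn. The pair is in the rejection region R if that p-value is ≤ 0.025. Then

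- power = sum over (x, y) in R of P(X = x | p1) × P(Y = y | p2)
- size = maximum of the same sum over a common rate p1 = p2 = p.

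**Step 1: reproduce the plan's main figures (46% v 17%).**

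| Split | Stated | Exact, one-sided 0.025 |
|---|---|---|
| 48/72 | 90% | 90.3% |
| 60/60 | over 90% | 91.1% |

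Both hold, so the method matches the plan's.

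**Step 2: the smaller effect (44% v 19%; stated: at least 80%).**

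| Calculation | 48/72 | 60/60 |
|---|---|---|
| Fisher, one-sided 0.025 | 78.9% | 79.9% |
| Fisher, two-sided 0.05 (minimum-likelihood p-value) | 80.9% | 79.9% |

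The shortfall at the stated level is 80 − 78.9 = 1.1 points at 48/72 and 80 − 79.9 = 0.1 point at 60/60. With unequal groups the two-sided p-value is not twice the one-sided one, so the two levels define different rejection regions. With equal groups they coincide, and two-sided 0.05 does not reach 80% either.

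For comparison, the pooled normal approximation at 48/72 uses a mean rate of 0.4 × 0.44 + 0.6 × 0.19 = 0.29:

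- null SE = √[0.29 × 0.71 × (1/48 + 1/72)] = 0.0846
- alternative SE = √[0.44 × 0.56/48 + 0.19 × 0.81/72] = 0.0853
- power = Φ[(0.25 − 1.96 × 0.0846)/0.0853] = Φ(0.99), about 84%.

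The gap between this and 78.9% is the price of Fisher's conservatism. Its maximum size at 48/72 is 1.67%, and 1.67/2.5 = 67% of the permitted level.

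**Step 3: dependence on N** (Fisher, one-sided 0.025, 44% v 19%, 40/60 split).

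| N | Split | Power |
|---|---|---|
| 120 | 48/72 | 78.9% |
| 124 | 50/74 | 79.95% |
| 125 | 50/75 | 80.4% |
| 134 | 54/80 | 83.6% |

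With this split, 80% is first reached at N = 125. The last row assumes that all 134 patients have a PRP result and that 40% are positive.

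**Step 4: the optional alternative.** Boschloo's test uses the Fisher p-value as its statistic and chooses the cut-off so that the maximum size over p is at most 0.025. It rejects whenever Fisher does.

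| Split, effect | Fisher | Boschloo | Boschloo maximum size |
|---|---|---|---|
| 48/72, 44% v 19% | 78.9% | 82.9% | 2.44% |
| 48/72, 46% v 17% | 90.3% | 92.6% | 2.44% |
| 60/60, 44% v 19% | 79.9% | 83.2% | 2.45% |

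At 48/72 and 44% v 19%, other unconditional exact tests give 81.4% with a pooled-Z ordering and 73.2% with an unpooled-Z ordering.

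**The case against.** The case for leaving the text alone is fairly strong.

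- **The miss is trivial.** It is 1.1 points, in a sentence that illustrates robustness for a secondary objective whose split and rates the plan itself calls unknown. The main figure reproduces. This stands, and it limits the point to a correction of wording.
- **The figure has a plausible source.** Two-sided 0.05 appears in the same section and gives 80.9% at 48/72. That may explain the number. But the sentence on level covers the PRP test and says one-sided 0.025, and at 60/60 the two-sided reading gives 79.9%.
- **More patients are planned.** If all 134 are analysed, Fisher clears 80% with no change of test. This stands under the assumptions in Step 3. The power text is nevertheless written for 120, and section 12.6 still says 120.
- **Fisher is a valid choice.** This stands too. Its conservatism is a known property, and the plan assesses the model itself by Brier score and AUC.

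Four stronger readings are tempting, and the documents do not support them. A reader might infer that the PRP comparison is underpowered, but its 90% design figure holds. A reader might infer that its size is fixed at 120, but 134 ccRCC patients are planned and section 12.8 takes all eligible registered subjects. A reader might infer that any unconditional exact test would restore 80%, but the unpooled-Z version falls to 73.2%. Finally, a reader might extend the criticism to the PD-L1 >20% v 0% contrast. Fisher gives 90.0% there (18 v 54, 55% v 13%), which matches the stated 90%, so there is no figure to correct.

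**Conclusion.** The concern holds in a narrow form. With the test, level and sample size that section 12.1 names, power for 44% v 19% is 78.9% at 48/72 or 79.9% at 60/60, not at least 80%. The result rests on N = 120 with every patient classified by PRP and 1-year PFS treated as a binary outcome known for all, as the plan's own calculation does. The statement becomes true at 48/72 under two-sided 0.05 (80.9%), or with 125 or more patients at a 40/60 split. It does not show that the sample size is inadequate or that Fisher's test is wrong. The importance is low: a stated figure should be corrected, and a modest gain of 2 to 4 points is available to the sponsor if wanted.

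**What to change.** **Correction, in section 12.1 and the synopsis.** Replace the 80% lower bound with about 79% for N=120 (48/72) at one-sided 0.025. Alternatively, state the N that will be analysed for PRP, including whether the 14 additional patients count, and quote the power for that N. This costs one edited sentence in two places.

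**Optional improvement.** Before outcome data are examined, prespecify Boschloo's test by name, at one-sided 0.025, for the PRP comparison and quote its power: 82.9% for 44% v 19% and 92.6% for 46% v 17% at 48/72. Name the statistic, because the gain depends on it. The cost is SAP wording and one function call in standard software. No patients are added and size stays at or below 2.5%. The downside is a test that some readers will know less well.

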12.2 Part B

Clear cell patients who reach best response of SD at 48 weeks or who experience progression will be offered the opportunity to enroll in the second component of the study, Part B, continued treatment with the addition of ipilimumab. The primary endpoint of this portion of the trial will be objective response (CR or PR) taking as baseline tumor measurements at the patient’s start of Part B. It is expected that roughly one-half of the Part A patients will be eligible for and choose to enroll in Part B, or roughly 60 total patients. A two-stage design will be used for this portion of the study where in the first cohort 29 patients will be accrued, treated and evaluated for response in order to provide guidance on whether to continue to enroll the entire cohort of 60 patients. The first stage analysis will be conducted without pausing accrual to Part B. If among the first 29 Part B patients there are at least 2 responses, there will be sufficient evidence to continue recruitment to Part B. With a true uninteresting response rate of 5%, there is a 57% chance of declaring the regimen uninteresting; however, with an interesting response rate of 20%, there is greater than 95% chance of continuing. If after enrollment of 60 patients there are at least 11 total responses, the lower limit on the 90% confidence interval for the true response rate will exclude 10% (ie, the 95% confidence interval will range from 10.6% to 28.5%, adjusted for the two-stage design). With 18 total responses, the 90% confidence interval on the true objective response proportion will exclude 20% (it, the confidence interval will range from 20.4% to 41.2%, adjusted for the two-stage design).

12.3 Non-clear cell (ncc) RCC: Part A

Subjects (comprising a heterogeneous group of histologies) will also be enrolled in the trial, at an accrual rate that is expected to be 33% that of clear cell patients. Therefore, an expected cohort of 40 nccRCC patients will be enrolled in the trial and analyzed separately for evidence of anti-tumor activity, principally focusing on overall response rate (CR or PR). With 40 patients, the 95% confidence interval on the true objective response proportion will be no wider than 32.4 percentage points and the probability of observing five or more responses under the hypothesis that the true response rate is 0.20 is at least 92%, hence there is high power to detect responses in

this cohort should the true response rate be interesting. Other endpoints of interest in this group of patients will include rates of SD and PFS at 1-year.

12.4 NccRCC patients: Part B

These subjects will also be available to enroll in Part B of the study. An estimated 20 patients will be enrolled and response rates in this resistant population will be reported. If no responses are seen in the first 14 patients that response rate will be deemed uninteresting. If any confirmed responses are seen accrual of ncc patients will continue for all eligible patients completing Part A.

12.6 Study Design

This is a phase II open-labeled study of single agent nivolumab involving two distinct groups of systemic treatment naïve patients – those with either metastatic clear cell (cc) or non-clear cell (ncc) RCC. One hundred and twenty patients will be accrued to the ccRCC group and up to 40 to the nccRCC group. Eligible patients will be enrolled at time of documented progression or prolonged SD, into Part B of the study, which involves the addition of ipilimumab to nivolumab. Part B will constitute a separate open-labeled phase II study with baseline parameters being reset at time of subject enrollment. With multicenter accrual of 6-7 patients per month, the study should accrue in 2 years.

12.7 Endpoints

12.7.1 Definition of Primary Endpoint

- PFS is defined as the time from Day 1 of treatment until the criteria for disease progression is met as defined by RECIST 1.1 or death as a result of any cause.
- The primary focus of this trial will be in the evaluation of PD-L1 expression levels to predict outcome. We expect that about 45% (or 54 expected) patients will have 0% PD-L1 and roughly 15% (or 18 expected) patients will express PD-L1 > 20%, which, given the sample size of 120 ccRCC patients provides 90% power using a 0.05 level two-sided test to test the hypothesis that PD-L1 >20% will be associated with significantly

improved 1-year PFS rate for patients treated with PD-1 blockade (55% vs 13% taken as a binomial quantity).

12.7.2 Secondary Endpoints

- Apply the PRP model, developed in the DF/HCC Kidney SPORE Project 4, to assign each patient a probability of having PFS > 1 year.
- The endpoint for Part B (addition of ipilimumab) will be objective response (CR or PR) taking as baseline tumor measurements at the patient's start of Part B.
- An expected cohort of 40 nccRCC patients will be enrolled in the trial and analyzed separately for evidence of anti-tumor activity, principally focusing on overall response rate (CR or PR).
- Toxicity by CTCAE criteria of nivolumab monotherapy in treatment naïve patients with cc and nccRCC.

12.8 Analysis Datasets

The primary analysis for both Part A and Part B will be the enrolled population comprising all subjects who meet eligibility criteria and are registered onto the study.

12.9 Assessment of Safety

This will be performed in all subjects that contribute data to the safety analysis e.g any subject who receives at least one dose of treatment on Part A of this protocol. The safety analysis for Part B will be considered separately and will include any subject who receives at least one dose of treatment on Part B. Safety will be assessed using the National Cancer Institute (NCI) Common Terminology Criteria for Adverse Events (CTCAE), v4.03. In addition, Immune Related Adverse events IrAE will also be recorded.

12.10 Assessment of Efficacy

All subjects with ccRCC who are registered on study will be assessed for progression free survival in order to determine the PFS rate at 1 year. Those patients who cross over to Part B of the study and have measurable disease will be assessed for tumor response using RECIST 1.1 with the pre-Part B tumor measurements serving as baseline.

All subjects with nccRCC who are registered on study will be assessed for tumor response using traditional RECIST 1.1 criteria both for Part A and Part B (if they have measurable disease at time of crossover).

12.11 Interim Analysis/Criteria for Stopping Study

A two-stage design will be used for Part B for the ccRCC population. In this study the first cohort 29 patients will be accrued, treated and evaluated for response in order to provide guidance on whether to continue to enroll the entire cohort of 60 patients. The first stage analysis will be conducted without pausing accrual to Part B. If among the first 29 Part B patients there are at least 2 responses, there will be sufficient evidence to continue recruitment to Part B. With a true uninteresting response rate of 5%, there is a 57% chance of declaring the regimen uninteresting; however, with an interesting response rate of 20%, there is greater than 95% chance of continuing.

13. TRIAL MANAGEMENT

13.1 Data and Safety Monitoring Plan (DSMP)

The study will be conducted with guidance from the Georgetown-Lombardi Comprehensive Cancer Center's (Georgetown LCCC) DSMP.

HCRN oversight activities include:

- Review all adverse events requiring expedited reporting as defined in the protocol
- Provide trial accrual progress, safety information and data summary reports to the sponsor-investigator
- Submit data summary reports to the lead institution Data Safety Monitoring Committee per Georgetown LCCC's DSMP.
- Submit data summary reports to the DSMC for review per DSMC SOP

13.2 Georgetown-Lombardi Comprehensive Cancer Center's Data Safety Monitoring Committee

HCRN will provide the following for the Georgetown LCCC's DSMC to review:

- Adverse event summary report
- Monitoring reports and audit results if applicable
- Data related to stopping/decision rules described in study design
- Study accrual patterns
- Protocol deviations

The Georgetown LCCC DSMC will review study data every quarter. Documentation of DSMC reviews will be provided to sponsor-investigator and HCRN. Issues of immediate concern by the DSMC will be brought to the attention of the sponsor-investigator and other regulatory bodies as appropriate. The sponsor-investigator will work with HCRN to address the DSMC's concerns.

13.3 Data Quality Oversight Activities

Remote validation of the EDC system data will be completed on a continual basis throughout the life cycle of the study. Automated edit check listings will be used to generate queries in the EDC system and transmitted to the site to address in a timely fashion. Corrections will be made by the study site personnel.

Monitoring visits to the trial sites may be made periodically during the trial to ensure key aspects of the protocol are followed. For cause audits may be performed as necessary. During onsite monitoring visits, source documents will be reviewed for verification of agreement with data entered into the EDC system. It is important for the site investigator and their relevant personnel to be available for a sufficient amount of time during the monitoring visits or audit, if applicable. The site investigator and institution guarantee access to source documents by HCRN or its designee.

The trial site may also be subject to quality assurance audit, as well as inspection by appropriate regulatory agencies.

13.4 Compliance with Trial Registration and Results Posting Requirements

Under the terms of the Food and Drug Administration Modernization Act (FDAMA) and the Food and Drug Administration Amendments Act (FDAAA), the sponsor-investigator of the trial is solely responsible for determining whether the trial and its results are subject to the requirements for submission to the Clinical Trials Data Bank, <http://www.clinicaltrials.gov>. All results of primary and secondary objectives must be posted to CT.gov within a year of completion. The sponsor-investigator has delegated responsibility to HCRN for registering the trial and posting the results on clinicaltrials.gov. Information posted will allow subjects to identify potentially appropriate trials for their disease conditions and pursue participation by calling a central contact number for further information on appropriate trial locations and study site contact information.

14. DATA HANDLING AND RECORD KEEPING

14.1 Data Management

HCRN will serve as the Clinical Research Organization for this trial. Data will be collected through a web based clinical research platform, a system compliant with Good Clinical Practices and Federal Rules and Regulations. HCRN personnel will coordinate and manage data for quality control assurance and integrity. All data will be collected and entered into the EDC system by study site personnel from participating institutions.

